7.1 DISCONTINUATION OF STUDY INTERVENTION

7.1.1 Definitive discontinuation

The IMP should be continued whenever possible.

In case the IMP is stopped, it should be determined whether the stop can be made temporarily; definitive IMP discontinuation should be a last resort. Any IMP discontinuation must be fully documented in the eCRF. In any case, the participant should remain in the study as long as possible.

Definitive intervention discontinuation is any intervention discontinuation associated with the definitive decision from the Investigator not to re-expose the participant to the IMP at any time during the study, or from the participant not to be re-exposed to the IMP, whatever the reason.

Discontinuation of study intervention for abnormal liver function should be considered by the Investigator when a participant meets one of the conditions outlined in [Section 10.6](#) or if the Investigator believes that it is in best interest of the participant.

If a clinically significant finding is identified in the ECG (including, but not limited to changes from baseline in QT interval corrected using Fridericia's formula [QTcF]) after enrollment, the Investigator or qualified designee will determine if the participant can continue in the study and if any change in participant management is needed. Review of ECG findings by a cardiologist needs to be taken into consideration for a decision of a definitive discontinuation of study intervention because of ECG changes. This review of the ECG printed at the time of collection must be documented. Any new clinically relevant finding should be reported as an AE.

See the schedule of activities (SoA) ([Section 1.3](#)) for data to be collected at the time of intervention discontinuation and follow-up and for any further evaluations that need to be completed.

Any abnormal laboratory value or ECG parameter will be confirmed within 24 hours to inform the decision whether to discontinue the IMP for the concerned participant.

In case of premature discontinuation of the intervention, the end-of-treatment visit will be conducted.

Handling of participants after definitive intervention discontinuation

Participants will be followed-up according to the study procedures specified in this protocol up to the scheduled date of study completion, or up to recovery or stabilization of any AE to be followed-up as specified in this protocol, whichever comes last.

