7.1.2 Temporary discontinuation

Temporary discontinuation of the IMP may be considered by the Investigator because of suspected AEs and/or laboratory abnormalities and/or ECG abnormalities AEs or disruption of the clinical trial due to a regional or national emergency declared by a governmental agency ([Appendix 9 \[Section 10.9\]: Contingency measures for a regional or national emergency that is declared by a governmental agency](#)) or another illness or if there is a need for a prohibited concomitant medication. Treatment can be resumed later when it is considered safe and appropriate. For all temporary discontinuations, the duration should be recorded by the Investigator in the appropriate pages of the eCRF.

Temporary discontinuation of the IMP decided by the Investigator corresponds to more than one missed dose.

The following shall lead to temporary treatment discontinuation:

- Cytopenia: follow Sanofi algorithm for neutropenia and thrombocytopenia as per [Appendix 6 \(Section 10.6\)](#).
- Serum creatinine, creatine phosphokinase (CPK) and liver enzyme increase: follow corresponding Sanofi algorithms as per [Appendix 6 \(Section 10.6\)](#).
- Cardiac arrhythmia (atrial fibrillation): Any Grade 3 event (symptomatic, urgent intervention indicated; device [eg, pacemaker]; ablation; new onset).
- Suicidal risk as per C-SSRS: if a participant scores “yes” on Items 4 or 5 of the Suicidal Ideation Section, or “yes” on any item of the Suicidal Behavior Section.

Analysis of missed doses will be described in the Statistical Analysis Plan.

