1.2 OBJECTIVES

1.2.1 Primary objectives

The primary objective of this study is to determine the long-term safety and tolerability of tolebrutinib in RMS patients.

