2.4.3 Extent of investigational medicinal product exposure and compliance

2.4.3.1 Extent of investigational medicinal product exposure for tolebrutinib

The extent of IMP exposure will be assessed by the duration of IMP exposure in LTS16004.

Duration of IMP exposure is defined as last dose date in LTS16004 - first dose date in LTS16004 + 1 day, regardless of unplanned intermittent discontinuations. Exposure will be summarized for the study as a whole and separately for Parts A and B. Part A exposure will be summarized according to tolebrutinib dose group (5, 15, 30, and 60 mg).

Overall duration of IMP exposure will be summarized descriptively as a quantitative variable (number, mean, SD, median, minimum, and maximum). In addition, duration of IMP exposure will be summarized categorically by counts and percentages for each of the following categories and cumulatively according to these categories:

- $0 < \text{Duration} \leq 24$ weeks
- $24 < \text{Duration} \leq 48$ weeks
- $48 < \text{Duration} \leq 72$ weeks
- $72 < \text{Duration} \leq 96$ weeks
- $96 < \text{Duration} \leq 120$ weeks
- $120 < \text{Duration} \leq 144$ weeks
- $144 < \text{Duration} \leq 168$ weeks
- $168 < \text{Duration} \leq 192$ weeks
- $192 < \text{Duration} \leq 216$ weeks
- $216 < \text{Duration} \leq 240$ weeks
- Duration ≥ 240 weeks.

For Part A exposure, 12-week intervals will be used.

Additionally for each exposure summary, the cumulative duration of treatment exposure will be provided, defined as the sum of the duration of treatment exposure for all participants, and will be expressed in participant years.

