2.4.5.1 Analyses of adverse events

Generalities

If an AE date/time of onset (occurrence or worsening) is incomplete, an imputation algorithm will be used to classify the AE as pre-treatment, TEAE or posttreatment. The algorithm for imputing date/time of onset will be conservative and will classify an AE as treatment emergent unless there is definitive information to determine it is pre- or post-treatment.

Adverse event incidence tables will present by primary SOC and PT, the number (n) and percentage (%) of participants experiencing an adverse event by tolebrutinib dose group, and overall. Multiple occurrences of the same event in the same participant will be counted only once in the tables. The denominator for computation of percentages is the safety population within each dose group/overall.

Summaries by primary SOC and PT will be presented by internationally agreed order of SOC and decreasing frequency of PT in the 60/60 mg tolebrutinib dose group within each SOC. Summaries by PT will be sorted by decreasing frequency of PT in the 60/60 mg tolebrutinib dose group.

Selected summaries (noted with an * below) will also be provided for Part A only. These tables will summarize incidence of adverse events by tolebrutinib dose group, namely, 5, 15, 30, and 60 mg, sorted by decreasing frequency in the tolebrutinib 60 mg dose group.

Analysis of all treatment-emergent adverse events

The following treatment-emergent adverse event summaries will be generated for the safety population:

- Overview* of treatment-emergent adverse events, summarizing number (%) of participants with any.
 - TEAE.
 - Treatment emergent SAE.
 - Severe TEAE.
 - AE leading to death.
 - TEAE leading to permanent treatment discontinuation.
 - TEAE considered by the investigator as related to IMP.
- All TEAEs by primary SOC and PT*.
- All TEAEs by PT.
- All TEAEs considered related to IMP (by the investigator) by primary SOC and PT.
- All TEAEs (for which intensity is collected) by maximal intensity (mild, moderate, severe), presented by primary SOC and PT.

Analysis of all treatment emergent serious adverse event(s)

- All treatment emergent SAEs by primary SOC and PT*.
- All treatment emergent SAEs by PT.
- All treatment emergent SAEs considered related to IMP (by the investigator) by primary SOC and PT.
- Listing of all SAEs including treatment emergent status.

Analysis of all treatment-emergent adverse event(s) leading to treatment discontinuation

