- All TEAEs leading to permanent IMP discontinuation by primary SOC and PT.
- All TEAEs leading to permanent IMP discontinuation by PT.
- Listing of all TEAEs leading to permanent IMP discontinuation.

Analysis of AESIs

- All treatment emergent AESIs by AESI category and PT* sorted by decreasing frequency of PT in the 60 or 60/60 mg dose group within each AESI category.
- Listing of all AESIs by AESI category including treatment emergent status.

Analysis of COVID-19 related AEs

- All treatment emergent COVID-19 related AEs by primary SOC and PT sorted by decreasing frequency of PT in the 60/60 mg dose group within each SOC.
- Listing of all COVID-19 related AEs.

Analysis of pre-treatment/post-treatment adverse events

- Pre-treatment and post-treatment adverse events, if any, including serious, will be summarized separately.
- Listing of all pre-and post-treatment adverse events.

Safety findings on MRI are collected as AEs on the eCRF and will be analyzed in together with other AEs.

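### The SAP counts AE-driven stopping only when it is permanent, so no planned output shows how often, why or for how long adverse events interrupted tolebrutinib

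*SAP*

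**What the plan says.** **Objective.** The trial is to "determine the long-term safety and tolerability of tolebrutinib in RMS patients" (SAP 1.2.1).

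**Protocol on stopping.** Section 7.1.1 asks sites to consider first whether a stop can be temporary, and says that "definitive IMP discontinuation should be a last resort". Section 7.1.2 introduces a list with "The following shall lead to temporary treatment discontinuation". The list covers cytopenia; rises in creatinine, CPK and liver enzymes; Grade 3 atrial fibrillation; and suicidal risk on the C-SSRS. The same section defines an investigator-decided temporary stop as more than one missed dose, has the duration of every such stop entered in the eCRF, and adds: "Analysis of missed doses will be described in the Statistical Analysis Plan".

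**SAP on stopping.** The AE overview has one row on stopping, "TEAE leading to permanent treatment discontinuation". The tables that follow are "All TEAEs leading to permanent IMP discontinuation by primary SOC and PT", the same by PT, and a listing, all for permanent stops (SAP 2.4.5.1). Disposition (SAP 2.2) likewise reports permanent discontinuation only.

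**SAP on exposure and missed doses.** Duration is last dose date minus first dose date plus one day, "regardless of unplanned intermittent discontinuations" (SAP 2.4.3.1). Compliance is the share of planned administrations taken as required, summarised by dose group with a count below 80% (SAP 2.4.3.2).

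**The concern.** The protocol steers sites towards temporary rather than permanent stops, while the SAP reports only the permanent ones. A liver, platelet or arrhythmia event that took a participant off drug for weeks, followed by restart, would look the same in the stopping tables as an event that needed no action. The weeks off drug would count as time on tolebrutinib.

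For a study whose primary objective includes tolerability, a reader would expect to learn how often adverse events interrupted treatment, for how long, and whether treatment was resumed. Permanent stops alone may say little: the protocol reports no TEAE leading to permanent discontinuation in the preceding trial (Protocol 2.3). The reason for each stop also matters. Protocol 10.8.1 adds temporary stops for prohibited co-medication at US and partial-hold sites, and these should not be confused with stops for an adverse event.

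**Working it through.** There is no planned figure to reproduce, because the documents give no frequency or length of interruptions. The check sets the texts side by side and then works out how far compliance and exposure could reveal an interruption.

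**1. What each output shows about a temporary stop for an AE**

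| SAP output | Shows the event? | Shows the stop? |
|---|---|---|
| TEAE, SAE and AESI tables (2.4.5.1) | yes | no |
| PCSA tables, liver plot and listing (2.4.5.3.1) | yes, where the criteria are met | no |
| C-SSRS summaries (2.4.5.3.2) | yes | no |
| Discontinuation row, tables and listing (2.4.5.1) | only if the stop is permanent | only if permanent |
| Exposure (2.4.3.1) | no | no |
| Compliance (2.4.3.2) | no | possibly, as missed doses without a reason |
| Listing of dosing irregularities (2.4.3.2) | no | only if a critical or major deviation |

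A stop that follows the protocol should not be a deviation, so the last row would not normally catch it. For Part A, the only stopping item marked for separate summary is the permanent-discontinuation row of the overview.

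**2. Can compliance stand in?**

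Inputs: a month is 28 days (Protocol 1.3) and the Month 60 target is Day 1680 (SAP Table 2), so 60 × 28 = 1680 planned daily doses.

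Compliance = 1 − missed days / 1680, if withheld doses count as planned:
- 4 weeks off: 1 − 28/1680 = 98.3%
- 12 weeks off: 1 − 84/1680 = 95.0%
- 24 weeks off: 1 − 168/1680 = 90.0%
- falling below 80% needs more than 0.20 × 1680 = 336 missed days, or 48 weeks

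If withheld doses do not count as planned, compliance does not move at all. The SAP does not say which applies.

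**3. Effect on exposure**

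Inputs: 126 enrolled (SAP 1.3). Assumptions: everyone is followed to Day 1680, and 10% to 20% of participants are off drug for 4 to 26 weeks.

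- Maximum gross exposure: 126 × 1680 / 365.25 = 579.5 participant-years
- Low end: 12.6 participants × 28 days / 365.25 = 0.97 participant-years; 0.97 / (579.5 − 0.97) = 0.2%
- High end: 25.2 participants × 182 days / 365.25 = 12.6 participant-years; 12.6 / (579.5 − 12.6) = 2.2%

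With 5% to 30% of participants off drug for 4 to 24 weeks, the same formula gives 0.08% to 3.1%. Over a short period an individual figure can be larger: a 4-week stop within an assumed 24 weeks overstates that participant's exposure by 28 / (168 − 28) = 20%.

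**The case against.** **The events are not lost.** They stay in the TEAE, SAE, AESI and PCSA outputs. Raised ALT, atrial fibrillation or flutter, and thrombocytopenia each have an AESI category. This stands. A reader might infer that interrupted cases vanish from the analysis; only their character as stops does.

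**The missed-dose commitment is met.** SAP 2.4.3.2 analyses missed administrations, and its SD and minimum respond to long gaps. This stands in part: the protocol promised an analysis of missed doses, and compliance is one, though thin. It would be wrong to say that the SAP contradicts the protocol. Compliance still carries no reason and no link to an adverse event.

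**Drug-related events should end as permanent stops.** Protocol 7.1.2.1 allows restart once the investigator judges IMP responsibility unlikely, and rules it out after an SAE that is related or of unknown cause. Such cases would reach the planned tables. This is the strongest point, and it means that the uncounted stops may be mainly ones not attributed to the drug. It does not remove the gap: the SAP reports TEAEs whatever their cause. Section 7.1.2 also words the restart condition more loosely, and those two passages should be reconciled.

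**Temporary stopping is not required for every named risk.** Protocol 10.6 makes its actions required only for ALT increase and thrombocytopenia and suggested otherwise, against the mandatory wording of 7.1.2. Severe infection and haemorrhage are not on the 7.1.2 list. This stands, and 7.1.2 and 10.6 also need reconciling.

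**Gross exposure does little harm.** AE percentages use the number of participants as denominator, exposure-adjusted summaries are only to be considered, and events arising during an interruption are also counted as treatment-emergent. This stands.

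**Conclusion.** The gap is real but limited. The SAP reports AE-driven stopping only when it is permanent, and no planned output gives the number, reason, duration or restart outcome of interruptions. Tolerability, part of the primary objective, is therefore described incompletely.

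A reader might go further and conclude that tolerability will look better than it is by some stated amount. The documents do not support that. The share of AE-related stops that the planned tables would capture needs counts of permanent and temporary stops, and neither is given; any percentage would only restate the assumed counts. The restart rule and the limited reach of the required actions in Protocol 10.6 leave the number of such interruptions open.

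The exposure effect is minor: about 0.2% to 2.2% over the whole study, assuming full follow-up of 126 participants and 10% to 20% of them off drug for 4 to 26 weeks. The reason to act is the missing description of interruptions, not the denominator. This is a worthwhile, inexpensive improvement; it does not invalidate the planned safety analysis.

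**What to change.** - **SAP 2.4.5.1:** add an overview row for TEAEs leading to temporary IMP discontinuation; a SOC/PT table of these by dose group and overall, also for Part A; and a listing with duration and restart status.
- **SAP 2.4.3.1:** summarise the number, reason and duration of temporary discontinuations, using the protocol's definition of more than one missed dose. Separate AE-driven stops from those for prohibited co-medication or an emergency. Show participant-years net of interruptions beside the gross figure.
- **SAP 2.4.3.2:** state whether doses withheld during a temporary stop count as planned administrations.

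The cost is SAP wording and a few tables. The protocol already requires the durations in the eCRF; the sponsor should confirm that the reason and the link to the AE are captured there too. The tolerability figures may look slightly less favourable. No clinical stopping or restart rule changes.

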2.4.5.2 Deaths

The following summaries of deaths will be generated for the safety population.

- The number of participants who died by study period ([Section 2.1.4.2](#)).
- Listing of all deaths including treatment emergent status and the tolebrutinib dose at the time of death.

2.4.5.3 Other Safety

2.4.5.3.1 Analyses of laboratory, vital signs and ECG variables

The summary statistics (including number, mean, median, Q1, Q3, standard deviation, minimum and maximum) of all laboratory values (central laboratory values and changes from baseline), vital signs, and ECG variables will be calculated for each visit or study assessment (baseline, each post-baseline time point) by tolebrutinib dose group and overall. Mean changes from baseline with the corresponding standard error may be plotted over time on treatment by tolebrutinib dose group for selected parameters.

The incidence of PCSAs at any time during the TEAE period will be summarized by (biological function for laboratory data) dose group and overall, whatever the baseline level and/or according to the following baseline status categories:

- Normal/missing.
- Abnormal according to PCSA criterion or criteria.

For laboratory parameters for which no PCSA criteria are defined, similar table(s) using the normal range will be provided.

Centralized data will be used preferentially to local measures when several measurements are performed on the same date and at the same time for a given laboratory test.

Potential drug-induced liver injury

The liver function tests, namely AST, ALT, alkaline phosphatase, and total bilirubin will be used to assess possible drug-induced liver toxicity.

In addition to the PCSA summaries, a graph of the distribution of peak values of ALT versus peak values of total bilirubin will be presented on a logarithmic scale. The graph will be divided into 4 quadrants with a vertical line corresponding to $3 \times \text{ULN}$ for ALT and a horizontal line corresponding to $2 \times \text{ULN}$ for total bilirubin.

A listing of all liver function values will be provided for any participant with a treatment emergent $\text{ALT} > 3 \times \text{ULN}$ and/or $\text{AST} > 3 \times \text{ULN}$ with bilirubin $> 2 \times \text{ULN}$ including the timing in terms of days on IMP.

